### 4.2 Per-Protocol Population

The per-protocol (PP) population for the crossover phase is a subset of the mITT population of the crossover phase and includes all mITT subjects without major protocol deviations that could impact the efficacy analyses. Subjects who are found to be <80% compliant with MS1819 during the crossover phase will be excluded from the PP population. The PP population will be used as supportive to the mITT population. Subjects will be included in the treatment sequence to which they were randomized regardless of the actual treatment sequence received.

The PP population for each stage of the extension phase is a subset of the mITT population of the extension phase and includes all mITT subjects without major protocol deviations that could impact the efficacy analyses. Subjects who are found to be <80% compliant with MS1819 during the relevant stage of the extension phase will be excluded from the PP population. The PP population will be used as supportive to the mITT population.

Prior to database lock, the protocol deviations will be reviewed and the PP Population will be determined for each phase.

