## 7. MEASUREMENTS OF TREATMENT COMPLIANCE

Treatment compliance will be summarized separately for each dose of the crossover phase and each dose of the extension phase.

For the crossover phase, treatment compliance will be summarized for MS1819 in terms of mg/day using a compliance rate. Given that subjects were to take the dose associated with their pre-study PERT during treatment with PERT, detailed pill information was not collected and thus compliance rate for PERT will not be summarized.

The compliance rate for MS1819 for the crossover phase will be calculated as:

$$[\text{Actual Dose mg/day} / \text{Expected Dose mg/day}] * 100$$

The actual dose (mg/day) a subject received will be calculated as:

$$[(\text{number pills dispensed} - \text{number of pills returned}) * 280 \text{ mg}] / \text{number of actual study days on MS1819 in the crossover phase,}$$

where the number of actual study days on MS1819 is calculated as:

$$((\text{date/time of last MS1819 dose} - \text{date/time of first MS1819 dose}) / 86400) + 1.$$

The expected dose for MS1819 is either 2240 mg/day or 4480 mg/day, depending on the randomized treatment assignment.

Treatment compliance will be summarized by each study period and overall for MS1819 using descriptive statistics.

As described in Section 4.2, subjects found to be <80% compliant with MS1819 during the crossover phase will be excluded from the PP population for the crossover phase.

Individual data for study drug (number of capsules) dispensed and returned and treatment compliance will be listed for all subjects in the mITT population for the crossover phase.

For the extension phase, treatment compliance will be summarized for MS1819 in terms of mg/day using a compliance rate.

The compliance rate for MS1819 for the extension phase will be calculated as detailed above, replacing 280 mg with 140 mg for the dose of each capsule.

The expected dose for MS1819 is either 4480 mg/day (4.4 grams/day) or 6720 mg/day (6.7 grams/day), depending on the stage of the extension phase.

Treatment compliance will be summarized for the extension phase using descriptive statistics.

As described in Section 4.2, subjects found to be <80% compliant with MS1819 during a given stage of the extension phase will be excluded from the PP population for that stage of the extension phase.

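### SAP 7 leaves the crossover day count in the extension compliance formula, so the rate as written does not measure compliance within an extension stage (minor correction)

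*SAP*

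**What the plan says.** SAP 7 defines the crossover rate as actual mg/day over expected mg/day. Actual mg/day is capsules dispensed minus capsules returned, times 280 mg, divided by the "number of actual study days on MS1819 in the crossover phase". A further line, beginning "where the number of actual study days on MS1819 is calculated as", sets that count as last minus first MS1819 dose date/time, converted to days, plus 1. This line names neither phase nor stage.

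For the extension the SAP makes two changes:

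- Capsule strength: "The compliance rate for MS1819 for the extension phase will be calculated as detailed above, replacing 280 mg with 140 mg".
- Expected dose: "The expected dose for MS1819 is either 4480 mg/day (4.4 grams/day) or 6720 mg/day (6.7 grams/day), depending on the stage of the extension phase".

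The divisor is not mentioned again. The rate then feeds an exclusion rule that is framed by stage. SAP 7 says that "subjects found to be <80% compliant with MS1819 during a given stage of the extension phase will be excluded from the PP population", and SAP 4.2 says the same: "Subjects who are found to be <80% compliant with MS1819 during the relevant stage of the extension phase will be excluded from the PP population".

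**The concern.** The formula has three inputs that depend on the phase: capsule strength, expected dose and days on drug. The extension text updates the first two and leaves the third pointing at the other phase. The crossover MS1819 period is planned at about 3 weeks and the extension at 2 weeks, so the divisor is usually too large and the rate too low.

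The rate is summarised for each extension dose, listed by patient, and used to decide who enters the per-protocol CFA and CNA summaries for each stage. Each stage has 9 to 14 patients, so one wrong exclusion removes between 1/14 = 7% and 1/9 = 11% of a stage.

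**Working it through.** **The plan's own figures.** Protocol Table 4 gives 32 or 48 capsules of 140 mg per day. 32 × 140 = 4480 and 48 × 140 = 6720 mg/day, so the expected doses in SAP 7 reproduce.

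**Inputs for the day counts**

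- Crossover confinement starts on Day 17 with a +5 day window, so Day 17 to 22 (Protocol 8.2, Visit 6), and lasts up to 7 days (Table 1, note D).
- The second marker is given on Day 4 of confinement (Protocol 8.3.3.1), and MS1819 continues until it has passed. I therefore assume at least 4 days of confinement.
- Extension confinement starts on E11 with a +4 day window, so E11 to E15, and lasts up to 7 days (Protocol Table 3, note C).
- I assume 12 hours between the clock times of the first and last dose. The SAP's date/time count for D dosing days is then (D − 1) + 0.5 + 1 = D + 0.5.
- The crossover range below comes from the first-period schedule. I use it for both sequences.

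**Dosing days**

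- Crossover: 17 + 4 − 1 = 20 to 22 + 7 − 1 = 28.
- Extension: 11 + 4 − 1 = 14 to 15 + 7 − 1 = 21.

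**Score of a fully adherent patient, formula as written.** Capsules per day × 140 equals the expected dose at both dose levels, so the dose cancels. With E extension days and D crossover days, the score is 100 × E / (D + 0.5).

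| E | D | Score |
|---|---|---|
| 14 | 20 | 14/20.5 = 68.3% |
| 14 | 21 | 14/21.5 = 65.1% |
| 14 | 28 | 14/28.5 = 49.1% |
| 17 | 20 | 17/20.5 = 82.9% |
| 17 | 21 | 17/21.5 = 79.1% |
| 21 | 20 | 21/20.5 = 102.4% |
| 21 | 28 | 21/28.5 = 73.7% |

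Counting dates only, without the half day, the 14-day scores are 70.0%, 66.7% and 50.0%, all still below 80%.

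**How often 80% is reached.** There are 8 values of E and 9 of D, so 72 combinations. A patient passes when E is at least 0.8 × (D + 0.5). The number of passing values of E is 5 at D = 20, 4 at 21, 4 at 22, 3 at 23, 2 at 24, 1 at 25, and none from 26 to 28. That is 19 of 72. This counts schedule combinations; it is not a forecast of the share of patients.

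**Score with days from the same stage.** 100 × E / (E + 0.5): 14/14.5 = 96.6% and 21/21.5 = 97.7%, or 100% on dates only. Every adherent patient passes at either dose.

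**The case against.** The strongest reply is that the intent is plain. SAP 7 opens by calling for separate compliance summaries by extension dose, restates the expected dose by stage, and closes with an 80% rule for compliance in a given stage. SAP 4.2 agrees. The day-count line names no phase, and SAP 8.2 already requires first and last dose dates for each extension dose. A programmer reading the whole section would probably use stage days. Per-patient compliance is also listed and the per-protocol set is settled before database lock, so an odd result in adherent patients could be noticed.

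That stands as evidence of intent, and it limits the seriousness. It does not remove the error: the formula as stated still names the crossover phase and does not yield the quantity that the exclusion rule needs.

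A reader might infer three stronger things that the documents do not support:

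- *Only the capsule strength is replaced.* The expected dose is replaced too, and the scores above already use it.
- *Adherent patients are dropped and the per-protocol set is nearly empty.* Exclusion follows only if the divisor is programmed literally. Even then, 14 days is the short end of 14 to 21, and some adherent patients pass.
- *The day count runs from the first crossover dose to the last extension dose, giving a far lower score.* That reading sets aside the phase named in the divisor. Neither document fixes a calendar start for the extension, so no figure can be attached to it.

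**Conclusion.** The point holds as an incomplete adaptation of a formula. Followed literally, SAP 7 scores a fully adherent 14-day patient at about 49% to 68%, and patients across the permitted schedule at about 49% to 102%. Per-protocol membership would then reflect lengths of stay in two phases. These figures rest on the 4-day minimum confinement, the 12-hour dosing day and the first-period crossover range.

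The consequence is limited. SAP 4.2 makes the per-protocol set supportive to mITT, and SAP 9.2.3 makes all extension efficacy analyses exploratory and descriptive. Neither document ties the dose step or the 5-patient expansion to the per-protocol set, and the crossover primary analysis is untouched. I rate it a minor correction.

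**What to change.** In SAP 7, state the extension rate for each stage as: capsules dispensed minus capsules returned in that stage, times 140 mg, divided by the days from first to last MS1819 dose in that same stage, divided by 4480 or 6720 mg/day as already given. State that this rate is the one used for the 80% rule in SAP 4.2.

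The divisor should name the stage and not merely the extension phase, because Protocol 11.3 lets patients treated at 4.4 g/day go on to 6.7 g/day. If capsules were counted by stage but days over the whole phase, two adherent 14-day stages with no gap would each score 14/28.5 = 49%.

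The cost is one or two sentences. Dispensing and returns are recorded at each stage's visits (Protocol Table 3), and dose dates are already listed by extension dose (SAP 8.2), so no new data are needed.

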## 8. SAFETY EVALUATION

### 8.1 Overview of Safety Analysis Methods

Unless otherwise stated, safety analyses will be presented separately for each dose of the crossover phase and each dose of the extension phase. For the crossover phase, all safety analyses will be performed using the safety population and summarized by actual treatment (MS1819 regardless of period vs. PERT regardless of period) allowing direct intrasubject comparison of the tolerability of MS1819 vs. PERT. For the extension phase, all safety analyses will be performed using the safety population and summarized for each dose. Safety measures summarized will include AEs, laboratory data, vital signs, and concomitant medications. Additionally, exposure to study treatment during the study will be displayed.

Safety data will not be imputed, except for partial and missing dates, which will be imputed only for defining treatment-emergent AEs (TEAEs) and concomitant medications. Imputed dates will not be presented in data listings.

TEAEs will be defined as any AEs that occur or are reported to worsen in severity on or after the date of first dose of study treatment in crossover phase period 1. Partial dates will be imputed for the purposes of defining TEAEs as follows:

- For a missing start day where the month and year are present, the start day will be set to the first day of the month, unless 1) the first day of the month is before the date of first dose of study treatment and the month and year are the same as the month and year of the date of first dose of study treatment, and 2) the end date is on or after the date of first dose of study treatment or the end date is completely missing, in which case the start day will be set to the first day of first dose of study treatment.
- For a missing start day and month where the year is present, the start day and month will be set to January 1st, unless 1) January 1st is before the date of first dose of study treatment and the year is the same as the year of the date of first dose of study treatment, and 2) the end date is on or after the date of first dose of study treatment or the end date is completely missing, in which case the start day and month will be set to that of the date of first dose of study treatment.
- For a missing end day where the month and year are present, the end day will be set to the last day of the month, unless the month and year are the same as the month and year of the last contact date for the subject, in which case the end day will be set to that of the subject's last contact date.
- For a missing end day and month where the year is present, the end day and month will be set to the subject's last contact date, unless the year of the subject's last contact date is greater than the end year, in which case the end day and month will be set to December 31st.

To categorize events with partial dates into their associated treatment periods, the imputation rules above will be defined relative to the first dose of the treatment period of interest separately (first treatment period of crossover, second treatment period of

crossover, 4.4 grams/day dose stage of the extension phase, 6.7 grams/day dose stage of the extension phase), as applicable. Thus, in the aforementioned rules, ‘study treatment’ refers to the treatment in the specified treatment period. Per the imputation rules, events with partial dates may require multiple imputed start dates to account for each treatment period. For example, an event with missing start day where the start month is the same as the treatment start month for both study treatments of the crossover period will have the start date imputed to both the treatment start date of the first crossover study period and the treatment start date of the second crossover study period.

Partial and completely missing dates will be imputed for the purposes of classifying concomitant medications as follows:

- Partial dates will be imputed following the same algorithm as above for TEAEs.
- For a missing start date (i.e., day, month, and year are missing), the start date will be set to the date of first dose of study treatment for each period (first treatment period of crossover, second treatment period of crossover, first dose period of the extension phase, second dose period of the extension phase), as applicable, unless the stop date is prior the date of first dose of study treatment for a given period, in which case the start date will be set to the stop date.
- For a missing stop date (i.e., day, month, and year are missing), the medication will be treated as ongoing.

## 8.2 Extent of Exposure

Time on treatment (weeks) will be calculated as (date of last dose of study drug – date first dose of study drug + 1)/7. Time on treatment will be summarized by treatment group for each period using descriptive statistics for all subjects in the safety population for the crossover phase. Time on treatment will be summarized using descriptive statistics for all subjects in the safety population for each dose in the extension phase. For subjects that participated in both the 4.4 grams/day period and the 6.7 grams/day period of the extension phase, time on treatment will also be summarized across both doses. Total time on treatment for MS1819 (across both doses of each the crossover phase and the extension phase) will also be summarized.

The date and time of the first and last dose of each study period will be presented in a data listing for all subjects in the safety population for each dose in the crossover phase. The date and time of the first and last dose will be presented in a data listing for all subjects in the safety population for each dose in the extension phase.

## 8.3 Adverse Events

Adverse events will be coded using the Medical Dictionary for Regulatory Activities (MedDRA) Version 23.0 to identify the system organ class and preferred term.

Adverse events that occur or are reported to worsen in severity on or after date of first dose of study treatment in crossover phase period 1 will be considered to be TEAEs.

TEAEs will be categorized as occurring in a given study period according to the following rules:

- Adverse events that occur or are reported to worsen in severity on or after date and time of start of crossover period 1 study treatment and on or before date and time of end of crossover period 1 study treatment will be attributed to crossover study period 1. Adverse events that occur or are reported to worsen in severity on the start date of crossover period 1 study treatment that do not have a time associated with the event will be attributed to crossover study period 1.
- Adverse events that occur or are reported to worsen in severity after the end date of crossover period 1 study treatment and on or before the date of end of crossover period 2 study treatment will be attributed to crossover study period 2. Adverse events that occur or are reported to worsen in severity on the date of end of crossover period 2 study treatment that do not have a time associated with the event will be attributed to crossover study period 2.
- Adverse events that occur on the crossover date between crossover study period 1 and crossover study period 2 that do not have a time associated with the event will be attributed to crossover study period 1.
- Adverse events that occur in both crossover study period 1 and crossover study period 2 will be attributed to both crossover study periods.
- Adverse events that occurred after the subject's last crossover study period will be classified as follow-up adverse events. If a subject entered both the first and second study periods, events occurring after the end date of the second study period will be considered as follow-up. If a subject discontinued prior to the start of the second crossover study period, any event occurring after the end date of the first crossover study period will be considered as follow-up. For subjects that did not enroll in the extension phase, any adverse event following the last crossover study period will be categorized as follow-up adverse events of the crossover phase. For subjects that did enroll in the extension phase, adverse events that occurred after the last crossover study period but before the start of the extension phase will be categorized as follow-up adverse events of the crossover phase.

The same period categorization rules will apply for the extension phase, where applicable, with the following exception. For the extension phase, if a subject only participates in the 4.4 grams/day dose stage of the extension phase, adverse events will only be categorized into the 4.4 grams/day treatment period or follow-up period within the extension phase. Otherwise, adverse events will be categorized into the 4.4 grams/day dose stage, the 6.7 grams/day dose stage, and follow-up as described above. For example, an adverse event that occurs in both the 4.4 grams/day dose period and the 6.7 grams/day dose period will be attributed to both extension phase treatment periods.

TEAEs will be summarized for all subjects in the safety population. TEAEs will be summarized by treatment group for each dose in the crossover phase and for each dose in the extension phase. The total number of TEAEs occurring will be shown. The number and percentage of subjects experiencing any TEAE will also be provided. In addition, summary tables will reflect a count and percentage of subjects experiencing at least 1 TEAE in each system organ class and preferred term. All percentages will use the number of subjects in the safety population as the denominator. Therefore, if a subject has more than 1 AE within a system organ class, the subject will be counted only once in that system organ class. If a subject has more than 1 AE that codes to the same preferred term, the subject will be counted only once for that preferred term. Tabular summaries will be sorted by descending frequency by system organ class and by preferred term in the MS1819 treatment group.

Treatment-emergent AEs will be presented by treatment group and overall for the crossover phase and overall for the extension phase with percentages that use the number of subjects in the safety population as the denominator.

Treatment-emergent AEs will also be summarized by maximum relationship to study drug and maximum severity. Relationship to each study treatment (MS1819 and prestudy PERT [crossover phase only]) will be scored as Related or Unrelated. Severity will be rated as Mild, Moderate, or Severe. All percentages will use the number of safety subjects as the denominator. Summary tables will reflect a count and percentage of subjects experiencing at least 1 TEAE in each system organ class, preferred term and grouping, relationship, or severity. If a subject experiences more than 1 AE within a system organ class or preferred term, that subject will be counted only once for that event under the maximum severity or most related category for the study drug. Similarly, in the event that relationship or severity data are missing, the study analysis will follow the assumption of maximum relationship or severity in the summary tables. These summaries will be presented by treatment group and overall in the crossover phase and overall in the extension phase with percentages that use the number of subjects in the safety population as the denominator. The tabular summaries will be sorted by descending frequency by system organ class and by preferred term in the MS1819 treatment group.

All AEs will be presented in data listings for subjects in the safety population.

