### **8.3 Second Treatment Period (Visits 7 [T], 8 [T] and 9)**

The second treatment period will begin once patients have passed their second blue dye marker at the end of V6, and the stool sample collection is complete. As soon as this has occurred, patients will crossover to their new treatment (either MS1819 or patient's prestudy porcine PERT).

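### SAP 8.3 ends period 1 by date and time but opens period 2 by date only, so first-dose-day events after a same-date switch can be missed from the MS1819 column

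*SAP*

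**What the plan says.** SAP 8.3 sets the periods with these rules:

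- Period 1 has a date-and-time upper limit. Events "on or before date and time of end of crossover period 1 study treatment will be attributed to crossover study period 1".
- Period 2 has date-only limits. It takes events that start or worsen "after the end date of crossover period 1 study treatment and on or before the date of end of crossover period 2 study treatment".
- The only rule specific to the switch day concerns "Adverse events that occur on the crossover date between crossover study period 1 and crossover study period 2 that do not have a time". These go to period 1.
- By contrast, events which "occur or are reported to worsen in severity on the start date of crossover period 1 study treatment that do not have a time" also go to period 1, which on that day is the treatment being started.
- "Adverse events that occur in both crossover study period 1 and crossover study period 2 will be attributed to both crossover study periods". The SAP does not say whether this refers to onset, worsening or duration.

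SAP 8.1 builds the crossover safety tables by actual treatment, so the assigned period decides the column. Where a partial date leaves the period open, SAP 8.1 can place an event in both; its example "will have the start date imputed to both the treatment start date of the first crossover study period and the treatment start date of" period 2.

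On the switch itself, Protocol 7.1 has no washout, and Protocol 8.3 ties the change to passage of the second dye marker at the end of Visit 6: "As soon as this has occurred, patients will crossover to their new treatment". Protocol 9.2 requires onset and resolution dates for adverse events and lists no onset time.

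**The concern.** The two limits do not meet. If the last period-1 dose and the first period-2 dose fall on one calendar date, part of that day lies after the end of period 1 and before the start of period 2. The untimed rule then assigns the whole day to the treatment being stopped.

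For a PERT-then-MS1819 patient, the day in question is the first exposure to the investigational product in this trial. An acute hypersensitivity reaction is the kind of event that could appear then, and Protocol 7.3.4 names an immunoallergic reaction as a reason for withdrawal. In an MS1819-first patient the same reaction on Day 1 is placed correctly, timed or untimed.

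Safety is a primary objective, and SAP 8.1 says the tables are meant to allow a within-subject comparison of tolerability. With about 15 patients per dose, one misplaced patient is visible in an incidence.

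**Working it through.** The plan states no figure for this point, so there is none to reproduce. The check applies the SAP 8.3 rules literally to one event: onset after the first MS1819 dose, on the date of that dose, in a PERT-then-MS1819 patient.

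**Illustrative timings**

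- Same-date switch: last PERT dose Day 22 at 08:00, first MS1819 dose Day 22 at 13:00.
- Next-date switch: last PERT dose on the evening of Day 21, first MS1819 dose Day 22 at 08:00.
- Where the event worsens later, it does so on Day 24.

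| Switch | Onset time | Worsens later | Period assigned | Reaches MS1819? |
|---|---|---|---|---|
| Same date | Timed | No | None | No |
| Same date | Untimed | No | 1 (PERT) | No |
| Same date | Timed | Yes | 2 | Yes |
| Same date | Untimed | Yes | 1 and 2 | Yes |
| Next date | Timed | No or yes | 2 | Yes |
| Next date | Untimed | No or yes | 1 and 2 | Yes |

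The last row takes the crossover date to be the first MS1819 date; the SAP does not define it. The event is missed from the MS1819 column in 2 of the 4 same-date cases. In the first row the follow-up category does not take it either, because that category starts after the patient's last crossover period.

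**Patients exposed.** SAP 2.4 allocates 1:1:1:1 to four arms, two of which give PERT first.

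- 30 completers × 1/2 = 15; per dose, 30 × 1/4 = 7.5.
- With the 36 planned enrolments of Protocol 7.3.1: 36 × 1/2 = 18; per dose, 36 × 1/4 = 9.

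**Events at risk.** The documents give no first-day reaction rate, so a range is assumed. Events at risk = 15 × rate:

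- 1%: 15 × 0.01 = 0.15
- 10%: 15 × 0.10 = 1.5
- 20%: 15 × 0.20 = 3

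At each assumed rate this is an upper figure for 15 patients: it takes every switch as same-date and no event as worsening later or being counted in both periods.

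**Effect on a table.** One patient among about 15 per dose is 1/15 = 6.7 percentage points of incidence.

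**The other sequence.** In MS1819-then-PERT patients, the untimed rule sends crossover-date events to period 1, which is MS1819, including events that began after PERT was resumed. A timed event after the switch again falls in no period.

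**Extension phase.** SAP 8.3 reuses the same period rules there where applicable. Patients go back to PERT at the end of Visit 13 (Protocol Table 3, footnote F). If the 6.7 g/day stage opens after the 4.4 g/day end date, events during the intervening PERT interval are charged to 6.7 g/day in any patient who takes both doses.

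**The case against.** A reader might infer that first-day reactions in PERT-first patients never reach the MS1819 column. The SAP does not support that. An event that worsens after the period-1 end date goes to period 2; one judged to occur in both periods counts in both; a partial date can be imputed to the period-2 start; and a timed event after a next-date switch goes to period 2. Same-date switching is likely but not certain, since doses go with meals and an evening marker stool could put the first dose on the next morning.

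Nor are the events lost altogether. Anything starting after the first period-1 dose is treatment-emergent, the tables include an overall summary, all adverse events are listed, and relatedness is scored separately for each treatment. An immunoallergic withdrawal would also appear among the reasons for withdrawal. The gap for timed events is probably a drafting slip: confining the switch-day rule to untimed events suggests timed ones were meant to be placed by time.

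A further inference would be that the tables are biased in favour of MS1819. The untimed rule works by sequence, so it also charges some PERT events to MS1819, and the documents give no rates from which to net the two. They also report a favourable safety record: no remarkable adverse events in the previous trial (Protocol 5.6.3) and no safety issues so far in this one (Protocol 11.2). Gastrointestinal examples are weak, because Protocol 9.1.1 keeps worsening pancreatic insufficiency out of the adverse event record unless it is serious.

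All of this limits the point. What remains is that the written rule leaves a timed event without a period and places an untimed one with the stopped treatment. The untimed case may be the usual one, given that the protocol asks only for dates. The two sequences do not offset each other for first-exposure reactions, because patients must have been on a stable PERT dose for at least 30 days before screening.

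It can also be said that the extension has no direct switch from 4.4 to 6.7 g/day. That is true, and it is why reusing a rule that opens the second stage when the first ends is unsuitable there.

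**Conclusion.** The defect stands and should be corrected. After a same-date switch, an event that follows the first period-2 dose and does not worsen later has no period if timed, and the old treatment's period if untimed. First-dose-day events on MS1819 in about 15 of 30 completers (7 to 8 per dose) can therefore be missed from the MS1819 column.

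The effect is on the by-treatment tables, not on the listings or the overall count. Its size depends on three quantities the documents do not give: the first-day reaction rate, the share of same-date switches and the share of events recorded with a time. The range of 0.15 to 3 events is an illustration and not an estimate. The documents support neither a claim that these events never reach MS1819 nor a claim of net bias in its favour. They do support the narrower statement that first-exposure reactions to MS1819 are the ones at risk.

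**What to change.** Amend SAP 8.3 as follows:

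1. Start period 2 at the date and time of the first period-2 dose, and let period 1 run up to that moment in patients who enter period 2. Timed crossover-date events are then placed by time, with no gap.
2. Count untimed crossover-date events in both periods, in line with the partial-date convention in SAP 8.1.
3. Define the crossover date, and say what it means for an event to occur in both periods.
4. Start each extension stage at its own first dose. Classify events between the stages as follow-up to the 4.4 g/day stage, as the SAP already does for events between the crossover and the extension.

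With these rules all 4 same-date cases in the table reach the MS1819 column. The cost is a few sentences of SAP text and no new dosing data, since SAP 8.2 already lists first and last dose dates and times. The downside is that an occasional background event will be counted in both columns.
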